5.0 STUDY PROCEDURES**5.1 Screening/Baseline Procedures**

Assessments performed exclusively to determine eligibility for this study will be done only after obtaining informed consent. Assessments performed for clinical indications (not exclusively to determine study eligibility) may be used for baseline values even if the studies were done before informed consent was obtained.

All screening procedures must be performed within 0 days prior to registration unless otherwise stated. The screening procedures include:

5.1.1 *Informed Consent***5.1.2 *Medical history***

Complete medical and surgical history, history of infections

5.1.3 *Demographics*

Age, gender, race, ethnicity

5.1.4 *Review subject eligibility criteria***5.1.5 *Review previous and concomitant medications*****5.1.6 *Physical exam including vital signs, height and weight***

Vital signs (temperature, pulse, respirations, blood pressure), height, weight

5.1.7 *Adverse event assessment*

Baseline adverse events will be assessed. See section 6 for Adverse Event monitoring and reporting.

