historical placebo-controlled trials with parameters listed in the table below and discussed in the introduction, the estimated pooled mean pain scores and (total variance) was 3.4 (1.50) in the placebo and 1.49 (1.77) in the UTAP groups. The random effects meta-analysis was conducted with the Comprehensive Meta-Analysis Software Version 3.3.070 (2013).¹²

Study name	Treatment	Mean	SD	Variance	Sample size
Hosgood (2012)	Placebo	3.70	2.00	4.00	22
Aniskevich (2014)	Placebo	4.00	2.30	5.29	11
Qu (2016)	Placebo	2.80	1.20	1.44	40
Fabrizio (2018)	Placebo	3.57	0.64	0.41	50
Random	Placebo	3.40		1.50	
Hosgood (2012)	UTAP	1.90	1.50	2.25	24
Aniskevich (2014)	UTAP	1.50	1.20	1.44	10
Qu (2016)	UTAP	0.84	0.59	0.35	40
Fabrizio (2018)	UTAP	1.80	0.82	0.67	50
Random	UTAP	1.49		1.77	

In accordance with ICH guidelines on statistical principles for clinical trials a type I error rate of 0.025 was used for this sample size calculation. Optimal sample size allocation was determined to follow a 2:2:1 ratio of LTAP:UTAP:Placebo. A total sample size of 235 is required with a 2:2:1 allocation ratio (94 LTAP, 94 UTAP and 47 Placebo) to achieve 90% power to establish non-inferiority of LTAP to UTAP with a fixed fraction of 0.50 (LTAP has to achieve more than 50% of the effect of UTAP compared to placebo to claim as non-inferior) assuming means and variances of 1.49 (1.77), 1.49 (1.77) and 3.40 (1.50) in the LTAP, UTAP and Placebo groups, respectively. This sample size calculation was performed using the PowerRet function of the 'ThreeArmedTrials' package with the following parameters:

```
power_RET(experiment = c(1.49,1.77), reference = c(1.49,1.77), placebo = c(3.4,1.5),Delta = 0.7, sig_level = 0.025, power= 0.9, allocation = c(2,2,1)/5,distribution = "normal")
```

The statistical evaluation will be performed in the first step by a two sample t-test for demonstrating superiority of UTAP over placebo. Group sample sizes of 94 and 47 for UTAP and placebo groups achieve over 99% power to reject the null hypothesis of equal or worse means when the population VAS pain score means (SDs) in the UTAP and Placebo groups are 1.50 (1.33) and 3.4 (1.22), respectively, with a significance level of 0.025 using a one-sided two-sample unequal-variance t-test. The calculation was performed with PASS Version 15.

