10.3 Data Analyses Plans

Analysis of Co-Primary Endpoints:

The distribution of VAS pain scores in each group will be examined and assessed for normality and homoscedasticity, visually, by generating probability-probability (P-P) plots, boxplots, stem-and-leaf plots and quantile-quantile (Q-Q) plots, and with the Shapiro-Wilk normality test. If necessary, a transformation of the data will be made to render appropriate for parametric testing. All analyses will be performed on patients who undergo surgery and have a 24 hour VAS pain score assessment. Balance on baseline characteristics (including gender, age at surgery, height, weight, BMI, and operative time) among the randomized groups will be assessed separately for each intervention, using the standardized difference. Any variable with an absolute standardized difference >0.52 (i.e., $1.96 \times 1/n_1 + 1/n_2$) for either intervention will be adjusted for in secondary analyses.^{13,14}

A step-down hierarchical hypothesis testing approach will be used to test the two hypotheses (co-primary endpoints). In the first step, to establish assay sensitivity, the alternative hypothesis that the 24-hour post-operative mean VAS pain score in the UTAP group is superior to that in the placebo group will be tested by a one-sided two sample t-test at the 0.025 level of significance ($H_{01}: \mu_{UTAP} \geq \mu_{Placebo}$ vs. $H_{A1}: \mu_{UTAP} < \mu_{Placebo}$).

If assay sensitivity is demonstrated in the first step by rejecting the null hypothesis, H_{01} , we will proceed to the second step of testing for non-inferiority of LTAP to UTAP. To establish non-inferiority, the alternative hypothesis that LTAP is non-inferior to UTAP will be tested using the ‘fractional approach’ introduced by Pigeot et al (2003) where the effect estimate is based on the ratio of the differences in means between LTAP and placebo and UTAP and placebo ($H_{02}: \frac{\mu_{LTAP} - \mu_{Placebo}}{\mu_{UTAP} - \mu_{Placebo}} \leq \theta$: vs. $H_{A2}: \frac{\mu_{LTAP} - \mu_{Placebo}}{\mu_{UTAP} - \mu_{Placebo}} > \theta$).

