θ is pre-specified as the fixed fraction of active reference effect (retention of effect) of 0.50 (LTAP has to achieve more than 50% of the effect of UTAP compared to placebo to claim as non-inferior). The second step will be carried out based on the Fieller’s one-sided 97.5% lower confidence bound for the ratio of $\mu_{LTAP} - \mu_{Placebo}$ and $\mu_{UTAP} - \mu_{Placebo}$. If the lower bound of the confidence interval is greater than 50% then the null hypothesis, H_{02} is rejected (LTAP (the experimental approach) retains more than 50% efficacy of UTAP (the active reference) then non-inferiority of LTAP to UTAP will be declared. The formula for calculating Fieller’s confidence bound is presented in Pigeot et al (2003) and will be implemented using The R package ‘ThreeArmedTrials’ developed by Tobias Muetze (2016).

Analysis of Secondary Endpoints:

The secondary endpoints of 24-hour cumulative post-operative opioid analgesic requirement expressed in morphine equivalent dose (MED), intraoperative time taken to complete the surgical block, total operating room time and surgical time will be summarized using median, 1st and 3rd quartiles and minimum and

maximum values. A Kruskal-Wallis analysis of variance will be used to compare the cumulative MED requirement (time to complete the surgical block, total operating room time and surgical time) among the three intervention groups with all pairwise comparisons made between groups using the Dwass-Steel-Critchlow-Fligner procedure (Dwass 1960; Steel 1960; Critchlow and Fligner 1991).¹⁵⁻¹⁷

The secondary endpoint of antiemetic medication use will be reported as the number and percentage of patients that require antiemetic medication during their hospital stay within each intervention group. A Chi-Square will be used to compare percentages across groups. A log-binomial regression model will be used to estimate and compare the prevalence ratios (PR) and corresponding 95% confidence intervals (CI) for antiemetic medication use among patients in the three intervention groups.

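### Covariates for adjustment are chosen by chance imbalance, not by expected link with 24-hour pain, so the adjusted analysis is not fixed in advance and available precision goes unused

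*Combined protocol and SAP*

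**What the plan says.** Section 10.3 (Analysis of Co-Primary Endpoints) looks at balance on a list, "including gender, age at surgery, height, weight, BMI, and operative time", using the standardised difference. The rule for adjustment is: "Any variable with an absolute standardized difference >0.52" in either intervention comparison is taken into the model, and only in secondary analyses ("for either intervention will be adjusted for in secondary analyses").

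Neither co-primary test uses a covariate. Superiority of UTAP over placebo "will be tested by a one-sided two sample t-test at the 0.025 level of significance". Non-inferiority of LTAP rests on Fieller's "one-sided 97.5% lower confidence bound for the ratio of" the two differences from placebo, computed from group means.

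The data for a fixed adjustment already exist. Section 5.1.3 collects "Age, gender, race, ethnicity", section 5.1.6 adds height and weight (hence BMI), and section 10.1 stratifies randomisation by type of surgery. One of the two references cited at the rule (reference 14) has a title about predictors of postoperative pain and analgesic use, yet no variable is selected because it predicts pain.

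**The concern.** A covariate improves a randomised comparison to the extent that it predicts the outcome. Observed imbalance says nothing about that: the rule can bring in a variable unrelated to pain and leave out one that is related but happens to be balanced.

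Three things follow.

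- **The adjusted analysis is not defined in advance.** Its covariates depend on the baseline data, the list is open-ended, and no adjusted model is written down. Height, weight and BMI could all enter together.
- **Precision is left unused.** Any variance in 24-hour VAS that age, BMI or type of surgery explains stays in the error term of both co-primary tests.
- **Imbalance below the trigger is not corrected**, even in a variable related to pain.

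**Working it through.** **Inputs.** Arm sizes "94 LTAP, 94 UTAP and 47 Placebo" (10.2); means 1.49, 1.49 and 3.40 and variances 1.77, 1.77 and 1.50 for LTAP, UTAP and placebo (10.2); one-sided alpha 0.025; retention fraction 0.50 in the text of 10.2 and 10.3, but 0.7 in the code line of 10.2. The share of VAS variance explained by covariates (R²) is not given. I assume 1-15%. The Time and Events Table schedules no preoperative VAS, so a low value is plausible.

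**1. The plan's cut-off.** Section 10.3 prints 0.52 as 1.96 × 1/n1 + 1/n2. I assume that a square root was lost:
- 94 v 47: 1.96 × √(1/94 + 1/47) = 1.96 × 0.1786 = 0.350
- 94 v 94: 1.96 × √(1/94 + 1/94) = 1.96 × 0.1459 = 0.286

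Neither gives 0.52, which would need about 2 × (1.96/0.52)² = 28 per arm.

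**2. How often a variable is flagged under randomisation.** Probability = 2 × [1 − Φ(cut-off / √(1/n1 + 1/n2))].

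| Cut-off | 94 v 47 | 94 v 94 |
|---|---|---|
| 0.52 | 0.52/0.1786 = 2.91, so 0.36% | 0.52/0.1459 = 3.56, so 0.04% |
| Formula value (0.350 / 0.286) | 5% | 5% |

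A simulation of 20,000 trials compared each block arm with placebo on the six variables (assumed: height, weight and BMI correlated; 15% of one sex). Some variable was flagged in about 4.4% of trials at 0.52 and in about 39% at 0.35. Correcting the cut-off changes the frequency but not the basis of selection.

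**3. Step 2 power without adjustment.** With θ the retention fraction, the effect is (1 − θ) × 1.91 and SE² = 1.77/94 + θ² × 1.77/94 + (1 − θ)² × 1.50/47.
- θ = 0.7: effect 0.573, SE √0.03093 = 0.176, power Φ(3.258 − 1.960) = 90.3%. The required total is 233 by the normal formula and 235 with a t distribution, so 0.7 reproduces the plan's 235.
- θ = 0.50: effect 0.955, SE √0.03152 = 0.178, power Φ(5.379 − 1.960) = 99.97%.

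**4. With adjustment.** SE is multiplied by √(1 − R²); the equivalent unadjusted total is 235/(1 − R²).

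| Assumed R² | SE multiplier | Equivalent N | Power, θ = 0.7 | Power, θ = 0.50 |
|---|---|---|---|---|
| 0 | 1 | 235 | 90.3% | 99.97% |
| 0.01 | 0.995 | 237 | 90.6% | 99.97% |
| 0.05 | 0.975 | 247 | 91.7% | 99.98% |
| 0.10 | 0.949 | 261 | 93.0% | 99.99% |
| 0.15 | 0.922 | 276 | 94.2% | 99.99% |

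**5. Imbalance below the trigger.** As an illustration, take an imbalance of 0.3 SD in a covariate correlated 0.3 with VAS. Given that imbalance, the between-arm difference shifts by 0.3 × 0.3 × √1.77 = 0.12 cm. That is 13% of the 0.955 cm allowance at θ = 0.50 and 21% of the 0.573 cm allowance at θ = 0.7. An imbalance of at least 0.3 SD in a given variable has probability 2 × [1 − Φ(0.3/0.1786)] = 9% (94 v 47) or 2 × [1 − Φ(0.3/0.1459)] = 4% (94 v 94).

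**The case against.** A pre-specified unadjusted primary analysis with adjusted secondary analyses is a legitimate design. Randomisation makes the unadjusted tests valid, and their standard errors already include chance covariate imbalance. Most candidates and the threshold are named before the data are seen, and selection uses no pain scores, so pain results cannot steer it. All of this stands. What it does not justify is imbalance as the criterion for entry, or an adjusted model that is never written down.

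Three stronger readings are tempting, and the documents support none of them.

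- **That covariates would almost never be used.** This depends on 0.52, which disagrees with the formula printed beside it. At the formula's own values each comparison flags a variable 5% of the time.
- **That the trial loses power it needs.** This holds only if 0.7 is the operative retention fraction. Under the stated 0.50, power is 99.97% without adjustment, and step 1 is stated to exceed 99%.
- **That age and BMI are known to predict pain in these patients.** The documents show only the title of reference 14 and give no R². At an R² of 0.01 the gain is negligible.

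**Conclusion.** The point holds as one of efficiency and pre-specification, not validity. The rule lets chance choose the covariates, confines them to secondary analyses and leaves the adjusted model open.

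The size of the loss depends on two things that the documents do not settle. For R² of 1-15%, fixed adjustment is worth about 2 to 41 patients (237 − 235 to 276 − 235). At a retention fraction of 0.7, power would be 90.6-94.2% instead of 90.3%. At 0.50 the benefit is a retention bound based on a standard error 0.5% to 8% smaller, with no useful change in power. A reader might infer bias in the co-primary tests from the 0.12 cm illustration. It is a shift in a between-arm difference conditional on a particular imbalance, and over repeated randomisations it averages to zero.

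The change is worth making because it costs little and must be settled before unblinded data are seen.

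**What to change.** Replace the imbalance trigger in section 10.3 with a pre-specified covariate-adjusted analysis of 24-hour VAS on arm, type of surgery (the stratification factor), age and BMI, whatever the observed balance. Within it:

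- Take the step 1 contrast and the step 2 Fieller bound from the adjusted arm means and their covariance matrix. Use a matrix that allows unequal variances, since section 10.2 plans step 1 with an unequal-variance t-test.
- Leave out operative time, which arises after randomisation and may be affected by the arm.
- Report the unadjusted tests alongside, and state in advance which of the two carries the confirmatory claim.
- Report standardised differences descriptively only.

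The cost is SAP wording and a little more code, because the adjusted Fieller bound must be computed from the model and not from the raw arm means. If the covariates turn out not to predict pain, a few degrees of freedom are lost. No new data or patients are needed.

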10.0 STATISTICAL CONSIDERATIONS**10.1 Study Design/Study Endpoints**

This is a single-center, single-blinded, (stratified) randomized placebo-controlled three-arm non-inferiority trial with 2:2:1 allocation ratio.

Randomization:

People who meet eligibility requirements and provide informed consent will be randomly allocated to 3 groups to receive either UTAP, LTAP or Placebo with a 2:2:1 allocation ratio. The allocation sequence will be stratified by type of surgery (prostatectomy or partial nephrectomy) using stratified block randomization with randomly varying block sizes. Random permuted blocks sizes within stratification groups will be used to minimize the chance of selection bias. Investigators will be blinded to the size of each block with only the study statistician responsible for generating the randomization list knowing this information. A randomization service called Sealedenvelope.com available at <https://www.sealedenvelope.com/simple-randomiser/v1/> will be used for allocation concealment to ensure that retrieval of the treatment group assignment is only revealed to appropriate team members on a real time basis after each new patient has been screened and consented. This service allows for allocation concealment that would not be possible if the entire randomization list was made available to team members at the beginning of the study. The security and integrity of the codes used by Sealedenvelope.com follows the Food and Drug Administration (FDA) standards for electronic records and follows the International Conference on Harmonisation Good Clinical Practice (ICH GCP) guidelines.

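### Surgery type stratifies the randomisation but enters neither primary test; if it predicts 24-hour VAS, both tests are conservative and the retention bound is wider than it needs to be

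*Combined protocol and SAP*

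**What the plan says.** Section 10.1 (Randomization): "The allocation sequence will be stratified by type of surgery (prostatectomy or partial nephrectomy) using stratified block randomization". Surgery type is the only stratification factor, and it is entered each time a patient is randomised.

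Section 10.3 gives the primary analysis in two steps.
- **Step 1** (UTAP superior to placebo) "will be tested by a one-sided two sample t-test at the 0.025 level of significance".
- **Step 2** (LTAP non-inferior to UTAP) uses Fieller's "one-sided 97.5% lower confidence bound for the ratio of" the LTAP-minus-placebo and UTAP-minus-placebo mean differences, computed with the ThreeArmedTrials package. The decision rule is: "If the lower bound of the confidence interval is greater than 50% then the null hypothesis" is rejected.

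No covariate is specified in either step. The one route to adjustment is in the same section: "Any variable with an absolute standardized difference >0.52" "will be adjusted for in secondary analyses". The check covers this: "Balance on baseline characteristics (including gender, age at surgery, height, weight, BMI, and operative time) among the randomized groups". Surgery type is not named there, although the list is not written as exhaustive.

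**The concern.** The trial forces balance on surgery type and then analyses the data as if it had not. The step 2 contrast is LTAP − θ·UTAP − (1−θ)·placebo, where θ is the retention fraction. Its coefficients sum to zero, as do those of the step 1 difference. When strata are balanced across arms, a surgery-type effect common to all arms therefore cancels from both estimates. The raw within-arm variances still contain it, so the standard errors are too large for the design used.

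The imbalance route cannot correct this. It leads only to secondary analyses, and stratified blocks make a standardised difference above 0.52 very unlikely for this factor.

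The stake is precision. If surgery type predicts VAS, the actual error rate falls below 2.5% and the reported retention bound is lower than the data support. If it does not, nothing is lost.

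**Working it through.** **Inputs (10.2).** Arm sizes are 94 LTAP, 94 UTAP and 47 placebo. The plan states its inputs as "assuming means and variances of 1.49 (1.77), 1.49 (1.77) and 3.40 (1.50) in the LTAP, UTAP and Placebo groups, respectively". The UTAP effect is 3.40 − 1.49 = 1.91 cm, and the one-sided level is 0.025.

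**The plan's own figures.** For a retention fraction θ and 2:2:1 allocation:

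N = (1.960 + 1.282)² × [1.77/0.4 + θ²·1.77/0.4 + (1−θ)²·1.50/0.2] / [(1−θ)·1.91]²

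- θ = 0.7, as in the printed software call: N = 232.6, so 233, or 235 in whole 2:2:1 blocks. Power at 235 is 90.3%. This reproduces the stated sample size.
- θ = 0.50, as in the text: N = 85.3, so 86. This does not reproduce 235. The mismatch between 0.50 and 0.7 is a separate matter, but it affects how much spare power there is.
- Step 1: SE = √(1.77/94 + 1.50/47) = 0.225 against 1.91 cm. Power is above 99.99%, consistent with the stated figure of over 99%.

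**Step 2 at θ = 0.50, unadjusted.** SE = √(1.77/94 + 0.25·1.77/94 + 0.25·1.50/47) = √(0.01883 + 0.00471 + 0.00798) = 0.1775. The contrast is 0.5 × 1.91 = 0.955. Power = Φ(0.955/0.1775 − 1.96) = 99.97%.

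**Effect of adjusting.** Let R be the share of within-arm VAS variance explained by surgery type, taken as equal in every arm and additive. The documents do not give R, so the values below are assumptions.
- Adjusted SE = 0.1775 × √(1−R).
- True error of the unadjusted test = Φ(−1.96/√(1−R)).
- Fieller lower bound r, if the observed means equal the planning values, solves 1.91(1−r) = 1.96 × √{(1−R)[1.77/94 + r²·1.77/94 + (1−r)²·1.50/47]}. The unadjusted bound is the R = 0 value, 0.815.

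| Assumed R | Adjusted SE (reduction) | True error, unadjusted | Fieller bound, adjusted |
|---|---|---|---|
| 0% | 0.178 (0%) | 2.5% | 0.815 |
| 5% | 0.173 (2.5%) | 2.2% | 0.820 |
| 10% | 0.168 (5.1%) | 1.9% | 0.824 |
| 20% | 0.159 (10.6%) | 1.4% | 0.834 |

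The error-rate column applies to both steps.

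**Simulation check.** Stratified blocks were simulated with 60,000 runs per cell, 50:50 and 30:70 surgery mixes, and R of 0, 5, 10 and 20%. Unadjusted error was 2.5–2.6%, 2.1–2.4%, 1.9–2.1% and 1.3–1.5%. Adjusted error was 2.4–2.6% in every cell. A separate run (20,000 trials per cell, 50:50 mix, R of 0, 10 and 20%) gave the same pattern, with adjusted error 2.3–2.6%.

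**Power.** With adjustment it is Φ(c/[SE√(1−R)] − 1.96). Without, it is Φ((c − 1.96·SE)/[SE√(1−R)]), where c is the contrast and SE the unadjusted standard error.
- θ = 0.50, planned effect: above 99.9% either way.
- θ = 0.50, UTAP effect 1.0 cm (assumption, c = 0.5): about 81 to 82%, 82 to 84% and 83 to 88% at R of 5%, 10% and 20%.
- θ = 0.7, planned effect: 91.4 to 93.0% at R = 10%, and 92.7 to 95.4% at R = 20%.

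**What the documents suggest about R.** The only hint is the four-trial table in 10.2. With a 50:50 mix, R = gap²/(4 × variance), using 1.50 for placebo and 1.77 for UTAP. Gaps are measured from the prostatectomy trial.

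| Comparison trial | Placebo gap (R) | UTAP gap (R) |
|---|---|---|
| Live-donor nephrectomy | +0.13 cm (0.3%) | +0.10 cm (0.1%) |
| Hand-assisted nephrectomy | +0.43 cm (3.1%) | −0.30 cm (1.3%) |
| Retroperitoneal surgery | −0.77 cm (9.9%) | −0.96 cm (13.0%) |

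The retroperitoneal approach is excluded from this trial (3.2.6). The other two trials give R of about 0.1% to 3%, an SE reduction of at most about 1.5%.

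**The case against.** The strongest reply is that no decision is likely to change. The planned tests are valid and pre-specified, the error rate is never above 2.5%, and a shift from 0.815 to between 0.820 and 0.834 is immaterial against a criterion of 0.50. This stands, and it is why the point is optional.

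The 5–20% shares are also hypothetical. With a 50:50 mix they need surgery-type gaps of about 0.55–0.59, 0.77–0.84 and 1.10–1.19 cm, which no eligible-type comparison in 10.2 shows. The signs also disagree between arms. Pooling the two nephrectomy trials by sample size gives 3.80 against 3.57 for placebo (R = 0.9%) and 1.78 against 1.80 for UTAP (R below 0.01%). On those figures, treating LTAP like UTAP, the SE falls by about 0.1% in step 2 and 0.3% in step 1. The 0.43 cm gap rests on 11 placebo patients in a trial that section 1.1 reports as median and IQR. All this stands as to size, although cross-trial gaps are weak evidence in either direction.

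Finally, an additive model may not fit, because section 4.1 describes block delivery that differs by surgery, and the simulations assumed no arm-by-surgery interaction. A custom computation also needs its variance estimator and degrees of freedom stated. These are requirements on the fix. They do not alter the fact that the unadjusted analysis discards a factor used in the design.

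**Conclusion.** The concern holds as a minor, optional improvement. The omission is plain from 10.1 and 10.3, and the direction is certain whenever a surgery-type effect common to the arms exists: both primary tests are conservative and the retention bound is wider than necessary. There is no bias and no added risk of a false non-inferiority claim.

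The size depends on an unknown share of variance. On the cross-trial evidence for eligible surgery (about 0.1–3%) it is nearly nil. At an assumed 10–20%, the true error is 1.9–1.4% and the standard error could fall by 5.1–10.6%. Power matters little at a retention fraction of 0.50 with the planned effect. It matters somewhat more if the UTAP effect is nearer 1.0 cm, or if the reconciled fraction is 0.7, where power at 235 is only 90.3% before any gain. Confidence in the practical importance is moderate, because the documents do not establish how far surgery type predicts VAS.

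**What to change.** In 10.3, pre-specify one linear model of 24-hour VAS on arm and surgery type, with residual variance allowed to differ by arm. Take the one-sided 0.025 UTAP-versus-placebo test from it. Compute the step 2 Fieller bound at 0.50 from its adjusted arm means and their covariance matrix. State the variance estimator and degrees of freedom in advance. Keep the planned t-test and the package's unadjusted bound as sensitivity analyses, and consider adding one that allows the arm effects to differ by surgery type.

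The cost is SAP wording and a short program for the adjusted bound, checked against the named package with no covariate in the model. No extra patients or data are needed, because surgery type is already recorded at randomisation. The change should be made before outcome data are seen.

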6.5 Stopping Rules

7.0 As none of the prior trials report any complications with TAP procedures, an acceptable AE rate would need to be very low i.e. <5% and include theoretical complications such as bleeding, or injection of anesthetic intravascularly. Most recent randomized trials^{3,4} do not report any complications with these injections. This trial will be monitored by the DSMB on a biannual basis and if a TAP procedure related serious complication occurs then accrual will be halted for safety considerations and a DSMB meeting requested.

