The secondary endpoints, including length of hospital stay and days to return of bowel function will be analyzed depending on existence of event censoring and/or occurrence of competing events at the time of analysis. Length of hospital stay will be calculated as the number of days between the date of surgery and the date of discharge from the hospital. Days to return of bowel function will be calculated as the number of days between the date of surgery and the date of first bowel movement. If the event is observed in all patients and there is no censoring at the time of analysis, the mean and standard deviation (if normally distributed) or median and IQR (if skewed) will be presented and an analysis of variance (or Kruskal-Wallis analysis of variance) will be used to compare means (or distributions) among groups, respectively. If the event is not observed in all patients (censoring at time of analysis) then the method of Kaplan-Meier will be used to estimate the median times to event and corresponding 95% confidence intervals will be constructed based on the method of Brookmeyer and Crowley.¹⁸ Comparisons of time to event distributions among intervention groups will be made with the log-rank test. If competing events are observed, such as death prior to the event of interest, then cumulative incidence functions (CIF) will be estimated in a competing risk setting. In these analyses, discharge and first bowel movement will be the defining events in each analysis while death without discharge or prior bowel movement will be considered the competing event. Patients who are alive and have not yet been discharged or have not had return of bowel function as of the data analysis cutoff will be censored. CIF comparisons among intervention groups will be made with Gray's test.¹⁹

The secondary endpoint of procedure related complications including bleeding or injection of anesthetic intravascular will be determined according to Common Terminology Criteria for Adverse Events (CTCAE v 4.0) and presented as frequency at each grade. A Poisson regression model will be used to test the difference in adverse event rates between the two groups. In this model, the numerator is the number of adverse events and the denominator (offset) is the natural log of the person days followed.

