11.3 Data Management and Monitoring/Auditing

10.3.1 Elements of a Data and Safety Monitoring Plan

List the name(s) of the individual(s) at the Icahn School of Medicine at Mount Sinai (ISMMS) who will be responsible for data and safety monitoring of this study. For each individual, indicate their role, name, title, and department information.

ISMMS Principal Monitor: (principal investigator)

Last Name: [name]

First Name: [name]

Academic Title: Assistant Professor
Department: Urology
Mailing Address: [name]
[contact]
E-mail: [name]

[name] is closely involved in the care of his patients and cares deeply that his patients, as well as those of his colleagues, are receiving the best possible care regardless of their involvement in a study.

Specific items that will be monitored for safety include adverse events, drop outs, and patient concerns. This information will be regularly reviewed biweekly during recruitment period. As participant involvement lasts no more than one week, this will assure that all subjects are being carefully monitored. Data accrued throughout the project will also be evaluated with the same regularity to ensure accuracy and completeness in reporting.

Should a temporary or permanent suspension of your study occur, in addition to the PPHS, the organization's IRB will be informed.

In addition, a DSMB of senior physicians in Urology and a biostatistician will monitor the study on a biannual basis.

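### The Poisson person-days test of block complications compares two unnamed groups in a three-arm trial and has no rule for arms with zero events, which are likely at low complication risks

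*Combined protocol and SAP*

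**What the plan says.** Section 10.3 (Analysis of Secondary Endpoints) introduces "The secondary endpoint of procedure related complications including bleeding or injection of anesthetic intravascular", to be graded by CTCAE v4.0 and "presented as frequency at each grade". It continues: "A Poisson regression model will be used to test the difference in adverse event rates between the two groups". In that model "the numerator is the number of adverse events and the denominator (offset) is the natural log of the person days followed". The section names no test statistic, significance level or contrast for this model, and no procedure for zero counts.

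Other parts of the document bear on this:

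- **Arms.** Section 10.1 describes a "three-arm non-inferiority trial with 2:2:1 allocation ratio", and section 10.2 sets 94 LTAP, 94 UTAP and 47 placebo. The analyses of opioid dose, times and antiemetic use in section 10.3 refer to all three groups.
- **Expected frequency.** Section 1.1 notes that the cited trials reported no injection complications. Section 6.5 says "As none of the prior trials report any complications with TAP procedures, an acceptable AE rate would need to be very low i.e. <5" per cent. No expected rate is given.
- **Follow-up.** Section 4.6 runs it through the inpatient stay to the first postoperative visit. Section 10.3.1 (data and safety monitoring plan) says "As participant involvement lasts no more than one week". The expedited-reporting note in section 6.3.4 uses 30 days.
- **Denominator.** Section 4.2 makes every treated patient evaluable for toxicity. Section 10.3 restricts all analyses to operated patients with a 24-hour VAS score, and section 4.8 removes patients who die, convert to open surgery or return to the operating room.

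**The concern.** A test between two groups is not specified when there are three. LTAP against UTAP, both TAP arms pooled against local injection, or another pair could each be chosen after the data are seen.

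The model also fits the endpoint poorly. Bleeding and intravascular injection arise at or near one injection, so the natural measure is risk per patient treated. Person-days bring in length of stay and visit timing, which the document describes inconsistently.

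The plan gives reason to expect very few such events. A Poisson rate ratio has no finite value when one compared arm has no events, and cannot be estimated at all when both have none. At stake is the only formal comparison of block complications: its result could depend on a software default rather than on a prespecified choice.

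**Working it through.** **Inputs.** Arm sizes 94, 94 and 47 are from section 10.2. The complication risk p is an assumption, because the document gives only none reported and a ceiling of under 5%. Risk is taken as equal across arms, with equal follow-up. The plan states no figure for this test, so there is none to reproduce.

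**Step 1: how often is an arm empty?** With Poisson counts, P(no events in an arm of n) = exp(-np). For p = 1%:

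- TAP arm: exp(-0.94) = 0.391. Placebo arm: exp(-0.47) = 0.625.
- At least one TAP arm empty: 1 - (1 - 0.391)² = 0.63.
- Both TAP arms empty: 0.391² = 0.15.
- Any of the three empty: 1 - (1 - 0.391)² × (1 - 0.625) = 0.86.

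| Assumed p | Expected events, two TAP arms | At least one TAP arm empty | Both TAP arms empty | Any of three arms empty |
|---|---|---|---|---|
| 0.5% | 0.94 | 86% | 39% | 97% |
| 1% | 1.88 | 63% | 15% | 86% |
| 2% | 3.76 | 28% | 2% | 56% |
| 5% | 9.40 | 2% | <0.1% | 11% |

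An empty TAP arm is more likely than not when (1 - exp(-94p))² < 0.5, that is, for p below about 1.3%. For context, no events among the 24 + 10 + 40 + 50 = 124 UTAP patients of the cited trials would give a one-sided 95% upper limit of 1 - 0.05^(1/124) = 2.4%. That reads no complications reported as zero.

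**Step 2: what does the model return?** With k events against 0, the log rate ratio is ln(k/T₁) - ln(0/T₂), which is infinite. Software stops at an arbitrary large value. For 6 against 0 in arms of 94 with equal person-days, the fit stopped at 22.4 with standard error about 17,985, so z is about 0.001. The likelihood-ratio statistic stays finite: 2k ln 2, on one degree of freedom.

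| LTAP–UTAP events | Wald p | Likelihood-ratio p | Fisher p |
|---|---|---|---|
| 0–0 | not estimable | not estimable | no evidence either way |
| 3–0 | 0.999 | 0.041 (statistic 4.16) | 0.25 |
| 6–0 | 0.999 | 0.004 (statistic 8.32) | 0.029 |

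The likelihood-ratio test is no safe default. With p = 2% in both TAP arms it rejects 9.6% of the time at a nominal two-sided 5% (level assumed; the plan states none).

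**Step 3: what does the offset do?** The rate ratio is (k₁/T₁)/(k₂/T₂). If mean follow-up is equal between arms, T₁/T₂ cancels and the offset is harmless. If length of stay, itself a secondary endpoint, differed by arm, equal risks per patient would appear as unequal rates. The document gives no figures from which to size this.

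**Step 4: what would exact limits give?** For zero events the two-sided 95% upper limit is 1 - 0.025^(1/n): 3.8% for 0/94 and 7.5% for 0/47. Exact limits exist whatever the counts.

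**The case against.** The strongest reply is that the plan never names the Wald test. A reader might infer that a 6–0 imbalance would be reported as p near 1. The document does not support that, since a likelihood-ratio test from the same model gives 0.004. What stands is that the statistic is unspecified and the candidates disagree widely.

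A reader might also infer that the test is undefined in the data most likely to arise. Strictly, that holds only when both compared arms are empty, and how likely this is depends on an assumed risk. An empty placebo arm does not prevent an LTAP–UTAP contrast. At the 5% ceiling an empty TAP arm is unlikely, though that figure is a limit of acceptability and not an expectation.

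The numerator may not be sparse. The paragraph moves from procedure-related complications to adverse events in general, section 2.4 joins the two, and section 6.3 follows events regardless of cause. If all adverse events are counted, the model may fit well. This stands, and it is why the counted event needs a definition.

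Harm from the offset is plausible but unquantified. Nor does the document make safety the main argument for the laparoscopic route: section 1.4 rests on operative time and pain control. The grade table and DSMB review would still show an imbalance.

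Finally, exact tests add little sensitivity: Fisher also misses 5–0 (p = 0.059).

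**Conclusion.** The point holds as a specification fault in a secondary safety analysis, worth correcting before the data are seen. That two groups are named in a three-arm trial, with no statement of which, follows from the text alone. So does the absence of a named test or a zero-count rule.

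The size of the sparse-data problem rests on assumed risks of 0.5% to 2%, equal risk and follow-up across arms, and a numerator limited to procedure-related complications. On those assumptions, at least one TAP arm is empty in 86% to 28% of trials, and the LTAP–UTAP contrast cannot be estimated in 39% to 2%.

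The primary analysis and the descriptive table by grade are unaffected.

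**What to change.** In section 10.3:

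1. Define the counted event, separating procedure-related complications from all-cause adverse events.
2. For procedure-related complications, replace the Poisson person-days test with the number and proportion of patients with at least one event, overall and by grade, in each of the three arms, with exact 95% confidence intervals.
3. Compare the three arms with an exact test, and give an exact interval for the LTAP minus UTAP risk difference.
4. Take as denominator all patients who received the assigned injection, consistent with section 4.2, and state that the 24-hour VAS restriction does not apply to this endpoint.
5. A Poisson model may be kept for all-cause adverse events, provided the three-arm contrast is named.

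The under-5% figure from section 6.5 may be shown beside the intervals as context, but should not become a pass/fail criterion: it comes from the stopping section and was not set as an analysis threshold.

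The cost is SAP wording only. The downside is that exact methods are conservative and have low power at these counts. For true risks of 5% against 1% in the two TAP arms, an exact conditional test at two-sided 0.05 has about 17% power. The main gain is therefore intervals that are valid at any count.
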